9.1.4 Change from Baseline and Percent Change from Baseline for ALP

A descriptive summary will be provided for ALP values, change from Baseline and percentage change from Baseline using 8-number summary by visit and treatment group.

Change from Baseline and percentage change from Baseline at Week 12 will be analyzed using an ANCOVA model with treatment as fixed effect and the associated baseline value as covariate. Least squares means and standard errors will be presented for each visit, p-value and 2-sided 95% confidence interval for treatment differences will be presented for each visit. Significance tests will be based on least-squares means using a two-sided $\alpha = 0.05$.

A by-subject listing will be provided for observed and derived variables.

Mean \pm SD ALP values and change from baseline by visit and treatment group will be plotted and also separately for the subgroups of UDCA and Fibrates strata. Scatterplots of the percentage change from baseline in ALP at Week 12 against the baseline ALP will also be produced.

Additional ALP endpoints investigated include:

- Decrease in ALP $\geq 10\%$ at 12 weeks
- Decrease in ALP $\geq 15\%$ at 12 weeks
- Decrease in ALP $\geq 20\%$ at 12 weeks
- Decrease in ALP $\geq 40\%$ at 12 weeks
- ALP < ULN and Decrease in ALP $\geq 10\%$ at 12 weeks
- ALP < ULN and Decrease in ALP $\geq 20\%$ at 12 weeks
- ALP < ULN and Decrease in ALP $\geq 40\%$ at 12 weeks
- ALP < 1.67xULN and Decrease in ALP $\geq 10\%$ at 12 weeks
- ALP < 1.67xULN and Decrease in ALP $\geq 20\%$ at 12 weeks
- ALP < 1.67xULN and Decrease in ALP $\geq 40\%$ at 12 weeks
- ALP < 2xULN and Decrease in ALP $\geq 10\%$ at 12 weeks
- ALP < 2xULN and Decrease in ALP $\geq 20\%$ at 12 weeks
- ALP < 2xULN and Decrease in ALP $\geq 40\%$ at 12 weeks
- Proportion of subjects at Week 12 with ALP <ULN, \geq ULN and <1.67xULN, \geq to 1.67xULN and < 2xULN and $\geq 2xULN$

ALP Shifts from baseline endpoints will also be evaluated as follows:

- Baseline ALP category ([1.67xULN,2xULN), [2xULN,3xULN), [3xULN,4xULN), [4xULN,5xULN), and $\geq 5xULN$) shifting to Normal, [1*ULN,1.67xULN), [1.67xULN,2xULN), and $\geq 2xULN$ (baseline categories are data dependent)

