#### 3.1 Subject Inclusion Criteria

Each subject must meet all of the following criteria to be enrolled into this study:

1. An informed consent document must be signed and dated by the subject
2. Male and female subjects of any ethnic origin between the ages of 18 and 75 years, inclusive
3. Male or female with a diagnosis of PBC by at least two of the following criteria:
  - History of ALP above ULN for at least 6 months
  - Positive Anti-Mitochondrial Antibodies (AMA) titers ( $>1/40$  on immunofluorescence or M2 positive by enzyme linked immunosorbent assay [ELISA] or positive PBC-specific antinuclear antibodies [PBC-ANAb])
  - Documented liver biopsy result consistent with PBC (with no cirrhosis)
4. For subjects with no documented liver biopsy performed within 2 years, subjects must undergo a transient elastography (Fibroscan) showing liver stiffness  $<14.0$  kPA
5. Must be on a stable dose of UDCA 12-20 mg/kg/day for at least 6 months prior to Screening or intolerant of UDCA in the opinion of the Investigator (no UDCA for at least 12 weeks prior to Screening)
6. Alkaline Phosphatase (ALP)  $\geq 1.67 \times$  ULN and/or total bilirubin  $>ULN$  but  $<2 \times$  ULN ( $<2.4$  mg/dL)
7. Subjects must have Screening laboratory values for Hepatitis B surface antigen (HBsAg), anti-HCV antibodies and HCV RNA negative, and Human Immunodeficiency Virus (HIV) 1 and 2 antibodies (Ab) as seronegative. NOTE: Subjects previously infected by chronic hepatitis C and treated with direct acting antivirals (DAAs) with sustained virologic response (SVR) for at least 3 years will be allowed.
8. Female subjects of childbearing potential must agree to use two effective methods of contraception from the date of Screening until 90 days after the last dose of EDP-305. Effective methods of contraception are defined as:
  - a condom for the male partner and at least one of the following for the female participant:
    - Intrauterine device
    - Oral, injectable, implantable, transdermal, or intravaginal hormonal contraceptiveNote: The above does not apply to female subjects of non-childbearing potential (ie, physiologically incapable of becoming pregnant) defined as:
  - has had a complete hysterectomy greater than or equal to 3 months prior to dosing or
  - has had a bilateral oophorectomy (ovariectomy) or
  - has had a bilateral tubal ligation or fallopian tube inserts or

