## **5.6 Treatment Assignment and Randomization**

Subjects will be randomized to study treatment using an Integrated Web Response System (IWRS). Subjects will be stratified initially by participation in the PK/PD substudy and then by a) prior use of fibrates and b) prior and/or current use of UDCA. Subjects will be randomized to the treatment groups shown below:

- Treatment Group 1 (N=45); EDP-305 1 mg orally for 12 weeks
- Treatment Group 2 (N=45); EDP-305 2.5 mg orally for 12 weeks
- Treatment Group 3 (N=15); Placebo (PBO) orally for 12 weeks

A minimum of 10 subjects per treatment group will be included in the PK/PD substudy. The randomization code will be produced by Enanta (or designee). The Enanta unblinded biostatistician or designee will review and approve the final randomization list.

During the Screening Period, subjects will be identified by a unique screening number assigned by the clinical site. Subjects who have completed screening assessments and are eligible for participation in the study will be randomized before the first dose of study drug (Day -1 or Day 1) and assigned a unique subject number which will be used to identify the subject throughout the study.

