### **11.5.2 Secondary Efficacy Endpoints**

The secondary efficacy endpoints are as follows:

- Bilirubin (Total, Conjugated, Unconjugated) decline from Baseline at Week 12
- Change from Baseline in Alanine aminotransferase (ALT), Aspartate aminotransferase (AST), and Gamma-Glutamyl transferase (GGT) at Week 12
- Change from Baseline of noninvasive liver fibrosis markers (Enhanced Liver Fibrosis [ELF] panel, PRO C3, AST to Platelet Ratio Index [APRI] and fibrosis-4 [FIB-4]) at Week 12
- Change from Baseline in fibrinogen, CRP, IL6, IL1 $\beta$ , TNF- $\alpha$ , TNF- $\beta$ , alpha2 macroglobulin and haptoglobin levels at Week 12

- Change from Baseline in Triglycerides (TG), Total Cholesterol (TC), High Density Lipoprotein Cholesterol (HDL-C), Low Density Lipoprotein Cholesterol (LDL-C) at Week 12
- Change from Baseline in 5D-itch scale and Visual Analog Score (VAS) at Week 12
- Change from Baseline in PBC-40 Quality of Life (QoL) at Week 12
- Pharmacodynamic parameters of EDP-305: FGF19, C4 and Bile Acid (BA) at week 12

Each endpoint will be summarized using an 8-number summary. Subjects in the efficacy population will be included. Comparisons of treatment arms will be performed using an analysis of covariance (ANCOVA) model with treatment and baseline values included in the model where appropriate.

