Any change to the data analysis methods described in the protocol will require an amendment ONLY if it changes a principal feature of the protocol. Any other change to the data analysis methods described in the protocol, and the justification for making the change, will be described in the clinical study report.

4 Study Objectives

The primary objective of the study is to evaluate the effect of EDP-305 on alkaline phosphatase (ALP) levels.

The secondary objectives of the study are as follows:

- To evaluate the safety and tolerability of EDP-305

- To evaluate the effects of EDP-305 on bilirubin levels
- To evaluate the effects of EDP-305 on other markers of liver function
- To evaluate the effects of EDP-305 on non-invasive markers of liver fibrosis
- To evaluate the effects of EDP-305 on inflammatory markers
- To evaluate the effects of EDP-305 on lipids
- To evaluate the effects of EDP-305 on pruritus
- To evaluate the effects of EDP-305 on Quality of Life (QoL)
- To evaluate the pharmacokinetics (PK) of EDP-305 and metabolites in plasma
- To evaluate the pharmacodynamics (PD) of EDP-305

5 Study Design

The study is a double blind, placebo-controlled study to compare 2 orally-administered dose levels (1 and 2.5 mg, respectively) of EDP-305 versus placebo for treatment of PBC.

The study is composed of 3 phases or periods:

- Screening period which includes the Screening Visit and may occur over a time period of 28 days prior to the first dose of study drug
- Treatment period which begins with the first dose of study drug on Day 1 and concludes with the End of Treatment (EOT) Visit on Day 84 (Week 12)
- Safety Follow-up period which includes the End of Study (EOS) Visit on Day 112.

Given that knowledge of ALP levels and other laboratory test results may lead to unblinding of treatment assignment, laboratory assessment data will remain blinded to the Enanta and PRA study blinded staff members by exclusion from scheduled data transfers, until after database lock. See Section 6.1.1 for a list of blinded laboratory test parameters.

Total planned enrollment is approximately 119 subjects based on a target of 105 after a 10% discontinuation rate. Enrollment will take place at approximately 90 sites located in the US as well as international locations (Australia, Austria, Belgium, Canada, France, Germany, Netherlands, Spain, and Great Britain).

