The total maximum length of time of participation for each subject enrolled in the study will be approximately 20 weeks based on a maximum of 28 days for the Screening Period, 12 weeks for the Treatment Period and 4 weeks for the Follow-up Period.

The planned sample size is approximately 105 subjects. Group sample sizes of 45 in each active arm and 15 in the placebo arm achieve 83.552% power to detect a ratio of the group proportions of 40%. The proportion in the smallest active arm is assumed to be 0.4000 under the null hypothesis and 0.0400 under the alternative hypothesis. The proportion in the placebo arm is 10%. The test statistic used is the two-sided Mantel-Haenszel test. The significance level of the test is 0.05.

To account for a 10% discontinuation rate, 14 additional subjects will be enrolled to attempt to have 105 who complete treatment, bringing the total number of subjects enrolled to 119.

PASS software version 14 was used to calculate the sample size.

Subjects will be asked to participate in the PK/PD substudy. The randomization schedule will be developed to allow for balance between the treatment groups within the substudy. For all non-PK/non-PD analysis purposes, the subjects in the substudy will be combined with the subjects not in the substudy.

In order to achieve this balance subjects will be stratified by:

- 1) prior use of fibrates
- 2) prior and/or current use of UDCA

Note that both 1) and 2) may be applicable for a given subject. In addition, a subset of subjects will be included in the PK/PD substudy.

Subjects will be randomized to 3 treatment groups in a 3:3:1 ratio after stratification:

- Treatment Group 1: EDP-305 1 mg orally for 12 weeks
- Treatment Group 2: EDP-305 2.5 mg orally for 12 weeks
- Treatment Group 3: Placebo (PBO) orally for 12 weeks

A minimum of 10 subjects per treatment group will be included in the PK/PD substudy.

Triangle Biostatistics generated the randomization schedule and provided it to Bioclinica as the IWRS vendor, for incorporation into the IWRS

6 Statistical Considerations

All analyses will use SAS version 9.4 or higher.

Continuous and discrete variables will be summarized using an 8-number summary (n, mean, standard deviation, median, 25th quartile, 75th quartile, minimum and maximum values). The median, minimum and maximum values will be displayed to the same level of precision as the raw data, the mean to one additional decimal place and the SD to two additional decimal places.

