9.1.2 Analysis of Primary Endpoint

For the primary endpoint, the Cochran-Mantel-Haenszel (CMH) test will be used to compare the proportion of subjects with ALP Response = "Yes" (percent improvement < -0.20 and/or normalization at Week 12 from Baseline) for each of the active treatment groups to placebo. The CMH test will be stratified, two-sided with an alpha level at 0.05. For the stratification in this analysis, the two randomization strata (fibrates and UDCA use) will be combined to create one strata variable. The code used to generate the p-value for each active treatment vs the placebo will be (with necessary output steps added):

Proc freq data=*indata*;

Tables strata*treatment*response/cmh;

Run;

The primary analysis of the primary endpoint will be performed using the Full Efficacy population. The analysis will be repeated on the Per-Protocol (PP) population, including only subjects with Baseline and Week 12 ALP results.

Subgroup analysis will be performed for ALP Response for the following subgroups:

- Age (<65 vs ≥65)
- gender
- UDCA strata
- Prior use of Fibrates strata
- ALP baseline categories [1.67xULN,2xULN), [2xULN,3xULN), [3xULN,4xULN), [4xULN,5xULN), and ≥5xULN (categories are data dependent)
- Total Bilirubin baseline categories [1xULN,2xULN), [2xULN,3xULN), ≥3xULN (categories are data dependent)
- ALP/Total Bilirubin/UDCA baseline subgroup (categories are data dependent, cut points should be based on median baseline values)
 - ALP≤3xULN, Total Bilirubin≤2xULN, UDCA usage,
 - ALP≤3xULN, Total Bilirubin>2xULN, UDCA usage
 - ALP>3xULN, Total Bilirubin≤2xULN, UDCA usage,
 - ALP>3xULN, Total Bilirubin>2xULN, UDCA usage
 - ALP≤3xULN, Total Bilirubin≤2xULN, No UDCA usage,
 - ALP≤3xULN, Total Bilirubin>2xULN, No UDCA usage
 - ALP>3xULN, Total Bilirubin≤2xULN, No UDCA usage,
 - ALP>3xULN, Total Bilirubin>2xULN, No UDCA usage

The code used to generate the p-value for each active treatment vs the placebo will be:

Proc freq data=*indata*;

Tables *subgroup**treatment*response/cmh;.

Run;

The subgroup analysis will be performed using the Full Efficacy population

The proportion of responders will be summarized and plotted by Visit.

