9.2.1.1 Bilirubin

A descriptive summary will be provided for Total, Conjugated and Unconjugated Bilirubin values, change from Baseline and percentage change from Baseline using 8-number summary by visit and treatment group.

Change from Baseline and percentage change from Baseline at Week 12 will be analyzed using an ANCOVA model with treatment as fixed effect and the associated baseline value as covariate. Least squares means and standard errors will be presented for each visit, p-value and 2-sided 95% confidence interval for treatment differences will be presented for each visit. Significance tests will be based on least-squares means using a two-sided $\alpha = 0.05$.

Additional endpoints for Bilirubin will include the following:

- Proportion of subjects at Week 12 with Total Bilirubin <ULN, \geq ULN and <1.5xULN, \geq 1.5xULN and <2xULN and \geq 2xULN.
- Shift in total bilirubin from baseline to Week 12 using the same categories as the endpoint in the previous bullet.

A by-subject listing will be provided for observed and derived variables.

Scatterplots of the change from baseline in total bilirubin versus the baseline total Bilirubin value will be produced.

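### Minor: the full-population ANCOVAs and the ALP sensitivity model do not name the fibrate and UDCA strata that the trial randomizes by; adding them costs almost nothing

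*SAP*

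**What the plan says.** Protocol 5.6 stratifies randomization first by PK/PD substudy participation "and then by a) prior use of fibrates and b) prior and/or current use of UDCA". SAP section 5 lists the same fibrate and UDCA factors. For the primary CMH test, SAP 9.1.2 says that "the two randomization strata (fibrates and UDCA use) will be combined to create one strata variable".

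The continuous endpoints are handled differently:

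- **ALP change and percent change (SAP 9.1.4):** the outcome "will be analyzed using an ANCOVA model with treatment as fixed effect and the associated baseline value as covariate". The strata appear in this section only as a way to split plots.
- **Secondary endpoints (SAP 9.2.1 to 9.2.12):** the same model throughout. For bilirubin, for example, "Change from Baseline and percentage change from Baseline at Week 12 will be analyzed using an ANCOVA model with treatment as fixed effect" and the baseline value as covariate.
- **Pharmacodynamic markers in the whole population (SAP 9.3.2.3):** the same model.
- **ALP sensitivity analysis by multiple imputation and MMRM (SAP 9.1.3):** no covariates are listed, so the strata are not named.

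Protocol 11.5.2 specifies an "analysis of covariance (ANCOVA) model with treatment and baseline values included in the model where appropriate". The SAP therefore agrees with the protocol. Neither document says why the strata are left out.

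**The concern.** Stratified randomization balances the arms on fibrate and UDCA history. If those factors also predict the outcome, a model that leaves them out keeps their variance in the error term, although the balanced design has already removed it from the treatment contrast. The reported standard errors are then somewhat too large. The primary test conditions on the strata, while the models behind the other efficacy p-values and intervals do not.

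What is at stake is a little precision and power. Precision is short here because every active-versus-placebo contrast rests on a small placebo arm: 15 of 105 planned, or 17 of 119 under 3:3:1.

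**Working it through.** **Plan's own figure.** There is none for these models. The only power figure, 83.552%, belongs to the primary binary test and is not used here.

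**Inputs from the documents.** Allocation 3:3:1; 119 enrolled, 105 expected to complete; two-sided alpha 0.05; stratification as in Protocol 5.6.

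**Assumptions (not in the documents).** Prior fibrate use pf = 10-20%. Off UDCA pu = 5-10%; Protocol 1.2.2 gives 5-10% UDCA intolerance, but for PBC patients generally. Permuted blocks of 7, 25% in the substudy, baseline slope 0.5, true effect 0 or 0.8 residual SD. The strata explain a share f = 0, 5% or 10% of the variance left after baseline.

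**Stratum effect implied by f.** With the same shift d (in residual SD) for each factor, d = sqrt[ f/(1-f) / (pf(1-pf) + pu(1-pu)) ].

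- At f = 0.05: sqrt(0.0526/0.1375) = 0.62 for 10%/5%, and sqrt(0.0526/0.25) = 0.46 for 20%/10%.
- At f = 0.10: 0.90 and 0.67.

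**Simulation.** 20,000 runs per setting, n = 119. Treatment + baseline is compared with the same model plus two main-effect strata terms.

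| pf / pu | f | Width ratio (with/without) | Type I error without / with | Power without / with |
|---|---|---|---|---|
| 10% / 5% | 0 | 1.004 | 0.048 / 0.048 | 0.802 / 0.799 |
| 10% / 5% | 5% | 0.978 | 0.046 / 0.050 | 0.781 / 0.795 |
| 10% / 5% | 10% | 0.952 | 0.041 / 0.049 | 0.772 / 0.806 |
| 20% / 10% | 0 | 1.003 | 0.048 / 0.048 | 0.803 / 0.801 |
| 20% / 10% | 5% | 0.977 | 0.047 / 0.051 | 0.790 / 0.803 |
| 20% / 10% | 10% | 0.950 | 0.040 / 0.049 | 0.770 / 0.803 |

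Mean estimates are 0.796-0.803 for a true 0.8 under both models, so neither is biased. Adding the strata gains 1.3-1.4 power points at 5% and 3.3-3.4 at 10%, and loses 0.2-0.3 at 0%.

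**Break-even.** A separate run at small f (4,000 per setting) gives a width ratio of 1 at f of about 0.8% for 10%/5% and about 0.5% for 20%/10%. The implied shifts are sqrt(0.00806/0.1375) = 0.24 SD and sqrt(0.00503/0.25) = 0.14 SD. Residual degrees of freedom fall from 119 - 4 = 115 to 113. Scaling width by degrees of freedom alone overstates the cost, because even two uninformative terms lower the residual sum of squares by 2/115 = 1.7% on average.

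**Fewer completers, combined stratum.** At n = 105 with rare strata (5-10% and 3%) and one four-level stratum (3 df), width ratios are about 0.981 at 5%, 0.955 at 10%, and 1.006-1.008 at 0%. Two main effects cost less and avoid empty cells.

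**PK/PD substudy.** At n = 30 (the stated minimum of 10 in each of three groups), uninformative strata widen intervals by about 2% and break-even is about 4-5%. If substudy allocation is also 3:3:1, 10 on placebo implies 30 + 30 + 10 = 70 subjects, and the cost would be smaller.

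**The case against.** The strongest reply is that nothing here is an error. Estimates are unbiased, the primary test is valid, and the SAP does what Protocol 11.5.2 says. This stands, and it is why the point is minor.

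A second reply is that the gain is assumed. No section gives the variance explained, the prior-fibrate share or this trial's off-UDCA share, and one value of f is unlikely to suit ALP, cytokines, lipids, itch and quality of life alike. This also stands. Reaching 5% needs shifts of roughly half a residual SD per factor. The low break-even answers it only in part: little is lost if the strata turn out not to matter.

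A third reply is that the strata are already visible in the primary test, the ALP-response subgroups and the ALP plots. True, but none of these sharpens the ANCOVA intervals.

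Three stronger readings are tempting, and the documents do not support them:

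- **The omission raises the false-positive rate or biases the estimates.** The effect runs the other way. Type I error of the planned model is at or below 0.05 in every setting.
- **The UDCA stratum has only one level.** Entry requires stable UDCA or being "or intolerant of UDCA in the opinion of the Investigator (no UDCA for at least 12 weeks prior to Screening", so a factor defined as "prior and/or current use of UDCA" could cover nearly everyone. No section gives the levels coded in the IWRS, so this is possible but not shown.
- **The SAP departs from the protocol.** On the ANCOVA terms the two agree.

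**Conclusion.** The point holds as a minor, nearly free improvement. The models for ALP change, the secondary endpoints and the full-population pharmacodynamic markers leave out two factors that the trial randomizes by, and the ALP sensitivity model does not name them.

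The likely size is 2.2-2.3% narrower intervals if the strata explain 5% of residual variance and 4.8-5.0% at 10%, against 0.3-0.4% wider if they explain nothing. The omission itself is certain from the text. The size of the gain is not, because it rests on assumed variance shares, stratum sizes and block size. No conclusion about the primary endpoint changes.

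**What to change.** - In SAP 9.1.4, 9.2 and 9.3.2.3, add the as-randomized fibrate and UDCA strata as two main-effect fixed terms. Use the same source variables as the CMH test, but not the combined variable.
- In SAP 9.1.3, name the same two factors in the imputation regression and in the MMRM.
- Leave the PK/PD substudy models in SAP 9.3.2.1 as they are. SAP 9.3.2.2 does not say which subjects it covers; state this, and add the terms only if it is the full population.
- In SAP section 5, state the UDCA levels coded in the IWRS. If there is only one, drop that term, or use the baseline UDCA usage (Yes/No) variable from SAP 8.1 as an ordinary prespecified covariate. The matching-to-randomization argument would not then apply to it.
- Leave the primary CMH test unchanged.

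**Cost.** SAP wording before database lock and unblinding, and a sentence in the study report. No new data are needed. Under SAP section 3, a change to the protocol's analysis methods "will require an amendment ONLY if it changes a principal feature of the protocol", and adding these covariates to supportive and secondary models should not count as one. The statistical downside, if the strata are uninformative, is about 0.3-0.4% wider intervals and 0.2-0.3 power points. If the sponsor prefers the current models, one sentence saying why would close the point.
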